13.2 Power and sample size

The overall sample size required for the BladderPath is 950 patients.

13.2.1 Feasibility stage

To evaluate the feasibility of setting up Imaging-directed pathway 2 (e.g. assessing effects of increased MRI demand), this stage will evaluate 150 patients entered into the study – approximately 50 from each of the three pilot sites. This will allow for qualitative checks of feasibility to be made; such as willingness of patients to be randomised into the study.

Quantitatively, we will consider feasibility to have been demonstrated if we observe at least 80% of possible MIBC patients correctly follow pathway 2. That is, patients receive an MRI at the appropriate pathway stage. Of the 150 patients recruited for this stage, 75 patients will be randomised to pathway 2. We expect that around 50% of the pathway 2 patients will be diagnosed as *possible MIBC*; which results in a sample of around 38 patients scheduled to have a MRI. The power of observing feasibility is dependent on the true proportion of patients who correctly follow the pathway. The probability of observing that 80% of the sample correctly follows the protocol for a selection of suitable true proportions is given in Table 5, which provides good power to detect feasibility.

Table 5.Probability of a successful feasibility stage given 80% of possible MIBC
patients are observed to correctly follow the pathway

True proportion	Probability of observing feasibility
80%	66%
83%	81%
85%	90%
87%	95%
90%	99%

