13. STATISTICAL CONSIDERATIONS

13.1 Definitions of outcome measures

The proportion of possible MIBC patients randomised to pathway 2 who correctly follow pathway protocol

Defined as the number of possible MIBC patients randomised to pathway 2 who have an MRI as a proportion of all possible MIBC patients randomised to pathway 2.

Time to definitive treatment

Defined as the interval in whole days between the date of randomisation and the first of: TURBT, systemic chemotherapy, radiotherapy, cystectomy or date of decision for best supportive care only.

Time to correct treatment

For NMIBC patients is defined as the number of whole days between date of randomisation and TURBT.

For MIBC patients is defined as the number of whole days between the date of randomisation and the first date of systemic chemotherapy, radiotherapy, cystectomy or date of decision for best supportive care only.

Clinical progression free survival

Defined as the number of whole days between date of randomisation and one of the following events, whatever occurs first:

- Diagnosis of distant metastases
- Diagnosis of loco-regional nodal recurrence
- Diagnosis of muscle invasive tumour recurrence in the bladder
- Diagnosis of non-muscle invasive tumour recurrence in the bladder
- Diagnosis of upper tract urothelial cancer or urethra
- Death from bladder cancer

Patients with no evidence of clinical progression will be censored at the last date of assessment or date of death if death is not attributed to bladder cancer.

Time to metastatic disease progression

Defined as the number of whole days between the date of randomisation and the date of detection of first distant progression or death from bladder cancer. Patients with no evidence of metastatic disease progression will be censored at the last date of assessment or date of death if death is not attributed to bladder cancer.

Time to loco-regional progression

Defined as the number of whole days between the date of randomisation and the earliest date of detection of loco-regional progression or death from bladder cancer.

Loco-regional progression is defined as recurrence in the bladder +/- local extension and

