13.3 Statistical analysis of efficacy and harms

13.3.1 Feasibility stage

Descriptive statistics on recruitment and consent rates will be calculated and assessed to ensure study feasibility. The numbers of patients assigned to each of the MIBC and NMIBC pathways in both arms will be calculated (i.e. numbers in each of boxes A-D in the study flow diagram). Of the patients who are initially given a diagnosis of possible MIBC (Box D), the proportion and 95% confidence interval (CI) of patients who correctly receive the MRI as planned will be calculated. The image-directed pathway will be considered feasible if this proportion exceeds 80%.

Secondary analyses

Other analyses at the feasibility stage will include descriptive statistics of the patients enrolled in the study and the proportions of each patient pathway (Boxes A-D) who correctly receive the allocated treatment pathway.

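### Table 5 gives the chance that at least 30 of 38 patients follow pathway 2, but 30 of 38 is 78.9% and does not meet the 80% feasibility rule

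*Protocol*

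**What the plan says.** The primary outcome of the feasibility stage is the proportion of possible MIBC patients on pathway 2 who follow it correctly (Protocol, Section 2.2, Table 2). Section 13.2.1 sets the success rule: "we will consider feasibility to have been demonstrated if we observe at least 80% of possible MIBC patients correctly follow pathway 2".

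The same section derives the sample. "Of the 150 patients recruited for this stage, 75 patients will be randomised to pathway 2". About half of these are expected to fall into the possible MIBC group, and the text draws the size of the evaluable sample from that share: "which results in a sample of around 38 patients scheduled to have a MRI". It then states: "The probability of observing that 80% of the sample correctly follows the protocol for a selection of suitable true proportions is given in Table 5". The table column headed "Probability of observing feasibility" reads 66, 81, 90, 95 and 99% for true proportions of 80, 83, 85, 87 and 90%, and the text describes this as good power.

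Section 13.3.1 repeats the rule with a strict inequality: "The image-directed pathway will be considered feasible if this proportion exceeds 80" per cent. Neither section prints the number of patients needed to pass.

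Section 13.1 defines the outcome: "Defined as the number of possible MIBC patients randomised to pathway 2 who have an MRI as a proportion of all possible MIBC patients". The denominator is limited to those allocated to that pathway.

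**The concern.** The first row of Table 5 is suspicious on its face. If the true proportion lies exactly on the threshold, the chance of reaching that threshold should be near one half; the table gives two in three. That suggests a cut-off below 80%.

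Table 5 is the only quantitative support for the statement that the feasibility stage has good power, and it concerns that stage's primary outcome. If it was computed for a different cut-off from the written rule, the chance of declaring feasibility is misstated. A result of 30 out of 38 would then be a success by the table's calculation and a failure by the text. That should be settled before data are seen.

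There is also a smaller wording point. Section 13.1 counts any MRI, whereas Section 13.2.1 asks that it be done at the right point in the pathway and Section 13.3.1 asks that it be received as intended.

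**Working it through.** **Inputs (Protocol, Section 13.2.1).** Patients on pathway 2: 75. Share with possible MIBC: about 50%. Hence n = 75 × 0.5 = 37.5, rounded to 38. Rule: observed proportion at least 80%. True proportions p: 80, 83, 85, 87 and 90%.

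**Cut-off implied by the rule.** 0.80 × 38 = 30.4, so at least 31 patients are needed. 31/38 = 81.6% passes; 30/38 = 78.9% does not. The strict inequality in Section 13.3.1 gives the same cut-off at n = 38.

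**Formula.** With X ~ Binomial(38, p), the probability of passing with cut-off r is P(X ≥ r) = Σ C(38, x) p^x (1 − p)^(38 − x), summed from x = r to 38.

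**Reproducing Table 5, then applying the written rule:**

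| True proportion | Table 5 | P(X ≥ 30) | P(X ≥ 31) | Table 5 minus P(X ≥ 31) |
|---|---|---|---|---|
| 80% | 66% | 65.5% | 50.0% | 16.0 points |
| 83% | 81% | 81.4% | 68.7% | 12.3 points |
| 85% | 90% | 89.4% | 79.9% | 10.1 points |
| 87% | 95% | 94.9% | 88.8% | 6.2 points |
| 90% | 99% | 98.9% | 96.8% | 2.2 points |

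The cut-off of 30 matches every row within 0.6 points. Apart from rounding, the overstatement is the probability of observing exactly 30, a result that fails the rule; at p = 80% this is 65.5 − 50.0 = 15.5 points.

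**Could another calculation explain the table?** Across n = 15 to 199, with all cut-offs from 70% upward, only 22/28, 26/33, 30/38 and 34/43 match all five rows within 2 points. All four cut-offs are below 80%. Among rules that respect 80%, the closest is 24/30, with a largest error of 5.3 points. A normal approximation at n = 38 gives 50% at p = 80%, or 58% with continuity correction, not 66%.

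**Sensitivity to n.** The sample is only about 38, so the at-least-80% rule was applied at neighbouring sizes:

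- For n = 30 to 45, the chance of passing at a true 80% runs from 46.6 to 60.7%, never 66%. At a true 85% it runs from 75.9 to 87.3%, never 90%.
- Averaged over n ~ Binomial(75, 0.5), the five probabilities are 53.2, 71.3, 81.8, 89.9 and 97.2%. Table 5 is then too high by 66 − 53.2 = 12.8, 81 − 71.3 = 9.7, 90 − 81.8 = 8.2, 95 − 89.9 = 5.1 and 99 − 97.2 = 1.8 points.

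**The two inequalities.** They agree at n = 38 but not where 80% of n is a whole number. At n = 40, at least 80% needs 32 (59.3% chance at p = 80%), while more than 80% needs 33 (43.7%).

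**The case against.** The arithmetic is hard to dispute, so the case on the other side concerns consequence and size.

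- **A reader might infer that the trial is more likely to be wrongly stopped.** The protocol does not support this. The stages overlap (Section 3), Section 13.3.2 allows the first two to run at the same time, and no section halts the trial if the proportion falls below 80%. The grounds on which the DMC may recommend discontinuation are recruitment, data quality and patient safety (Section 15.5). This objection stands: only the chance of declaring feasibility is misstated.
- **A reader might take 16 points as the general error.** That gap belongs to the row where truth equals the threshold. It falls to about 10 points at 85% and 2 at 90%. After correction, the claim of good power still holds reasonably well at 85% and above. This also stands.
- **The corrected figures depend on n.** They do, so they should carry n as an assumption. But no n from 30 to 45 restores the 66% or the 90%, so the direction does not depend on it.
- **A reader might infer from Section 13.1 that a patient resected first and scanned later counts as adherent.** That follows only if the definition is read alone. The outcome's title, Sections 13.2.1 and 13.3.1, and the description of pathway 2 in Section 7.2 point the other way. What stands is a looseness of wording, not a demonstrated flaw in the result.

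The 150-patient size is not derived from Table 5 and no comparison between arms uses it, so correction leaves the design untouched.

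**Conclusion.** The point holds. Table 5 reports the probability for a cut-off of 30 out of 38, which does not satisfy the protocol's own rule in either of its wordings. At n = 38 the true chance of declaring feasibility is 50, 69, 80, 89 and 97%, against 66, 81, 90, 95 and 99% stated. At a true proportion of 85%, the risk of missing the criterion is about 20%, twice the 10% the table implies. At 83% the chance is 69%, which is not good power.

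This rests on independent patients with a common probability of following the pathway, and on n = 38. The cut-off of 30 is inferred because the protocol prints none, but at n = 38 it is the only one that fits all five rows.

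**What to change.** Keep the 80% rule as a proportion, since the denominator is not fixed in advance and a rule written only for 38 patients might never apply. Replace the Table 5 column with 50, 69, 80, 89 and 97%, stating n = 38 and a cut-off of 31 as assumptions; the averaged values (53, 71, 82, 90 and 97%) could be added. Limit the statement about good power to true proportions of about 85% or more. Use the same inequality in Sections 13.2.1 and 13.3.1.

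If 30 of 38 was the intended pass mark, keep the table and restate the threshold consistently in both sections.

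Separately, word the definition in Section 13.1 so that it agrees with Sections 13.2.1 and 13.3.1 on when the MRI must take place. The sponsor should settle that wording; the protocol does not itself state a test based on TURBT.

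The cost is one table column and a few sentences, with no change to design, sample size or data collection. The stated probabilities become less favourable.

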13.2.2 Intermediate stage

In this stage, we check that pathway 2 will reduce the TTDT for MIBC patients compared to pathway 1. The estimated sample size for this stage is event driven and requires at least 20 MIBC patients to have definitive treatment across both treatment arms.

To account for patients with longer times on the waiting list being prioritised for treatment, we first assume that the hazard of treatment changes over time and follows a Weibull distribution in both treatment arms. We further assumed that the TTDT in pathway 1 has a median of 100 days and 95th percentile 150 days and the effects of pathway 2 is to reduce the median TTDT to 70 days. Assuming that the distribution of the TTDT pathway 2 follows a Weibull distribution with the same shape parameter as pathway 1 and that the usual proportional hazards assumption holds; the hazard ratio for the two study arms is 3.6. Hence, using the log-rank test, to have 80% power to detect a hazard ratio of 3.6 would require a total of 20 patients with MIBC and to have 90% power would require a total of 20 patients. Around 20-25% of new BC patients present with de novo MIBC. Hence, to recruit a total of 20 MIBC patients, *approximately 80-100 patients will need to be recruited*. At 90%, this would increase to approximately 130 patients.

13.2.3 Definitive stage

This stage tests the effect of the new image-directed pathway on the longer term clinical endpoints. The anticipated duration is 30 months in 15 regional referral centres. The estimated total sample for this stage is *380 progression events*; or approximately 950 patients with bladder cancer.

For this stage, the primary outcome is clinical progression-free survival and is designed to detect a reduction in progression events in pathway 2 such that the hazard ratio is 0.75. Assuming that the

proportional hazards assumption holds; to detect a hazard ratio of 0.75 with 80% power requires observation of 380 progression events and with 90% power requires observation of a total of 510 progression events. To detect this effect at 2 years follow up, assuming an overall recurrence rate of 40%, will require 950 (80% power) or 1275 (90% power) patients. Similar to the intermediate stage, the power for this stage is event driven and hence will depend on the number of observed events and not the number of patients recruited.

13.3 Statistical analysis of efficacy and harms

13.3.1 Feasibility stage

Descriptive statistics on recruitment and consent rates will be calculated and assessed to ensure study feasibility. The numbers of patients assigned to each of the MIBC and NMIBC pathways in both arms will be calculated (i.e. numbers in each of boxes A-D in the study flow diagram). Of the patients who are initially given a diagnosis of possible MIBC (Box D), the proportion and 95% confidence interval (CI) of patients who correctly receive the MRI as planned will be calculated. The image-directed pathway will be considered feasible if this proportion exceeds 80%.

Secondary analyses

Other analyses at the feasibility stage will include descriptive statistics of the patients enrolled in the study and the proportions of each patient pathway (Boxes A-D) who correctly receive the allocated treatment pathway.

13.3.2 Intermediate stage

Kaplan-Meier estimates of TTDT for MIBC patients in each arm will be evaluated. To compare the TTDT for MIBC between arms, a Cox regression model will be constructed. Covariates added to the model will include: patient age, gender and study centre.

Secondary analyses

Intermediate stage secondary analyses will include a Cox regression model comparing the TTDT of all possible MIBC patients (i.e. not just those confirmed as MIBC patients but all patients that pass through box B and box D in the study flow diagram).

Descriptive statistics of pathway use will be updated from the feasibility stage, if the two stages do not occur simultaneously.

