Title	BladderPath: Image Directed Redesign of Bladder Cancer Treatment Pathways	
Design	Open label, multi-stage randomised controlled study with three overlapping stages: feasibility, intermediate and final efficacy stage	
Patient population	Newly diagnosed bladder cancer patients	
Sample size	Feasibility stage – 150 patients Intermediate stage – event driven, at least 20 MIBC patients (approximately 80-100 patients will need to be recruited overall). Final clinical stage – event driven, at least 380 progression events, (approximately 950 patients)	
Inclusion Criteria	 Patients attending clinic for the investigation of symptoms suspicious of bladder cancer (initial consent process) Patients given a diagnosis of suspected bladder cancer and requiring a transurethral resection of a bladder tumour (TURBT) based on visual cystoscopic examination of the bladder (confirmatory consent process, post cystoscopy) Provision of written informed consent 	
Exclusion Criteria	 Patients unable or unwilling to undergo MRI Previous diagnosis of bladder cancer Previous entry in the present study 	
Aim	The aim of the BladderPath study is to improve staging, accelerate treatment and reduce iatrogenic tumour spread in patients with muscle invasive bladder Cancer (MIBC) by avoiding TURBT, ultimately improving clinical outcomes. The hypothesis being tested is that substituting TURBT with multiparametric magnetic resonance imaging (mpMRI) (pathway 2) will avoid unnecessary surgery and reduce the time to definitive radical treatment for MIBC	
Primary Outcomes	Feasibility stage : proportion of possible MIBC patients randomised to pathway 2 who correctly follow the protocol Intermediate stage : time to definitive treatment for all possible MIBC patients Final clinical stage : clinical progression-free survival	
Study duration	60 months	
Study Office contact details	Cancer Research UK Clinical Trials Unit (CRCTU) Institute of Cancer and Genomic Sciences University of Birmingham [name] [contact] [contact] E-mail: [contact] Website: www.birmingham.ac.uk/bladderpath	

Study Schema

Schedule of Events

Visit No.	1	2	2	3	4
Visit Reason	Clinic visit for investigation of symptoms suspicious of bladder cancer	MRI	TURBT	DTT ¹	Follow-up ²
Informed consent 1	\checkmark				
Informed consent 2	\checkmark				
Medical history	\checkmark			✓	
Inclusion/exclusion criteria	\checkmark				
Biopsy	\checkmark				

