Appendix	x 1 - World Medical Association Declaration of Helsinki	39	
	Appendix 2 - Definition of Adverse Events 42		
Appendix	x 3 - Common Toxicity Criteria Gradings	42	

BACKGROUND AND RATIONALE 1.

Background 1.1

Bladder cancer is the fifth most common cancer in western society, with a rising global incidence and 430,000 new cases in 2012^{1,2}. In the UK there are approximately 10,000 new cases and 5,000 deaths attributed to bladder cancer annually³. In western populations, over 90% of bladder cancers are urothelial cell carcinoma (UCC). Standard management follows a pattern established during the 1950s with the development of the rigid cystoscope. Prognosis has not improved in the last 30 years³⁻⁵.

Standard management involves a pathway of diagnostic flexible cystoscopy followed by a transurethral resection of the bladder tumour (TURBT) with a rigid cystoscope. TURBT has the multiple purposes of diagnosis, staging and treatment of non-muscle invasive bladder cancer (NMIBC), i.e. removal of the tumour. Further treatment such as radical cystectomy or chemoradiotherapy is then necessary for muscle invasive bladder cancer (MIBC).

For MIBC, this initial TURBT often understages invasion (up to 30% of MIBCs are initially staged as high grade NMIBC at first TURBT)⁶, and may contribute to extra-vesical tumour dissemination through bladder perforation or venous emboli generated through the high-pressure resection process⁷. Crosssectional pelvic imaging after TURBT impedes the accuracy of staging due to surgical artefacts (such as perivesical inflammation and reactive lymph nodes)⁸⁻¹¹.

Typically, the need for a TURBT, histopathological review and MDT decision-making adds at least 6-12 weeks to the pathway, prolonging the delay to commencing (the most appropriate) definitive radical treatment for patients with MIBC^{6, 12-14}.

An ideal pathway would separate NMIBC patients from MIBC patients at the time of diagnosis. Faster and more accurate application of established technologies would streamline therapy, potentially improve outcomes and save clinical costs.

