2.2 Outcome Measures

The primary and secondary outcomes change as we go through the study. These are summarised in Table 2.

	Primary Outcomes	Secondary Outcomes
Feasibility stage	The proportion of possible MIBC patients randomised to pathway 2 who correctly follow pathway protocol	 Overall proportion of patients who correctly follow protocol Recruitment and retention rates at each study site Counts of each definitive treatment
Intermediate stage	The time to definitive treatment (TTDT) for all possible MIBC patients	 TTDT for all patients TTDT for probable NMIBC patients Proportion of all patients who correctly follow pathway protocol Recruitment and retention rates at each study site
Final clinical stage	Clinical progression-free survival (CPFS)	 Cost effectiveness of each pathway Patient Quality of life The proportion of patients who correctly follow pathway protocol

Table 2.Primary and Secondary Outcomes

1 1	TTDT for all a socible MIDO a stights
	TTDT for all possible MIBC patients
	 TTDT for all probable NMIBC patients
	TTDT for all MIBC patients
	TTDT for all NMIBC patients
	Time to correct treatment
	Time to each treatment type
	Time to recurrence, progression or metastatic disease progression
	Number of recurrences; progressions and incidence of metastatic disease
	Number of each type of treatment(s) received
	 Accuracy of MRI/TURBT by comparison with histological confirmed diagnoses
	Overall and disease specific survival
	Number of unnecessary radical cystectomies
	Number of SAEs

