7.6 Compliance

All analyses will be by intention to treat. The initial feasibility stage will assess compliance with the protocol and feasibility of implementation.

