13.4 Planned subgroup analyses

Subgroup analyses will be conducted in the definitive stage according to:

- Initial diagnoses: possible MIBC or probable NMIBC
- Final diagnosis type: MIBC or NMIBC

- Multifocal vs. single invasive cancer
- Men vs. women
- Age stratified

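### The intermediate primary outcome is set in possible MIBC patients, but the main analysis and the power use confirmed MIBC, a group settled only after randomisation

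*Protocol*

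**What the plan says.** **Declared primary outcome.** Protocol section 2.2, Table 2, gives the intermediate primary outcome as "The time to definitive treatment (TTDT) for all possible MIBC patients". The synopsis agrees: "time to definitive treatment for all possible MIBC patients". Possible versus probable status is the clinician's assessment at cystoscopy and is a minimisation factor (6.1.2), so it is known before allocation.

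**Main analysis.** Section 13.3.2 opens with a different group: "Kaplan-Meier estimates of TTDT for MIBC patients in each arm will be evaluated", followed by "To compare the TTDT for MIBC between arms, a Cox regression model will be constructed". A Cox model in possible MIBC patients then appears under secondary analyses. It is described as covering "not just those confirmed as MIBC patients but all patients that pass through box B and box D in the study flow diagram".

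**Power.** Section 13.2.2 derives a hazard ratio of 3.6 and a requirement of 20 patients with MIBC for 80% power. It converts this to 80-100 recruits with the 20-25% share of new patients who have MIBC. Section 13.2.1 puts the possible-MIBC share at about 50%; that figure is not used here.

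**Staging routes.** In pathway 1 stage comes from TURBT (7.1). In pathway 2, possible MIBC patients have mpMRI in place of TURBT (7.2).

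**Principle.** Section 7.6: "All analyses will be by intention to treat".

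**The concern.** Two faults meet here.

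First, the protocol names one primary population and analyses and powers another. The stage exists to check whether pathway 2 shortens TTDT, and the answer could depend on which section the analyst follows.

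Second, the group that 13.3.2 uses is formed after randomisation. Among patients randomised as possible MIBC, those later called MIBC are found through TURBT in one arm and through a route that begins with mpMRI in the other. If the two routes pick up different fractions of true MIBC, the arms being compared are selected differently. The protocol itself expects such a difference: it says "up to 30% of MIBCs are initially staged as high grade NMIBC at first TURBT" (1.1) and gives mpMRI a sensitivity of 94% (1.4). A comparison restricted in this way sits badly with 7.6.

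**Working it through.** **1. Reproduce the plan's figure.** Inputs from 13.2.2: Weibull times, pathway 1 median 100 days and 95th percentile 150 days, pathway 2 median 70 days, same shape. Allocation is 1:1 (6.1.2). Alpha is not stated; two-sided 5% is assumed.

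- Shape = ln(ln 20 / ln 2) / ln(150/100) = 3.61.
- Hazard ratio = (100/70)^3.61 = 3.62, against the stated 3.6.
- Schoenfeld events at 80% power = 4 × (1.960 + 0.842)² / (ln 3.6)² = 19.1, rounded up to 20. Power at 20 events is 81.7%; a simulated log-rank test at 20 events gives 75%.
- Recruits = 20/0.25 to 20/0.20 = 80 to 100.

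The stated numbers reproduce, and the 20-25% conversion shows that they refer to patients with MIBC. (At 90% power the formula gives 26, and 26/0.20 = 130 matches the recruits stated there, but not the 20 patients stated for 90%. That is a separate slip.)

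**2. Size of the declared primary population.** 80-100 recruits × 50% = 40-50 possible MIBC patients. If all MIBC falls in this group, 20%/50% to 25%/50% = 40-50% of them truly have MIBC. The protocol gives no hazard ratio for this mixture.

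**3. Power in that population.** The truly MIBC part keeps the medians of 100 and 70 days. The non-MIBC part is assumed to have the same shape and the medians shown. There were 3,000 log-rank tests per setting, two-sided 5%, with every patient having an event.

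| Share truly MIBC | Non-MIBC median, pathway 1 / 2 (days) | Average HR | Power, 40 patients | Power, 50 patients |
|---|---|---|---|---|
| 50% | 30 / 30 | 1.80 | 34.5% | 44.3% |
| 50% | 70 / 70 | 2.00 | 51.9% | 61.3% |
| 50% | 100 / 100 | 1.51 | 29.5% | 32.7% |
| 40% | 30 / 30 | 1.58 | 21.5% | 28.1% |
| 40% | 70 / 70 | 1.77 | 38.0% | 46.8% |
| 40% | 100 / 100 | 1.37 | 20.1% | 24.2% |
| 50% | 30 / 60 | 1.38 | 11.3% | 14.4% |
| 40% | 30 / 60 | 1.08 | 7.0% | 6.0% |

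With equal non-MIBC timing, power is about 20-61%. The pairs that hold exactly 20 MIBC patients are 40 patients at 50% (about 30-52%) and 50 patients at 40% (about 24-47%). The last two rows assume that pathway 2 delays treatment of the non-MIBC part; power is then far lower.

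**4. What 80% would take.** Schoenfeld events are 66 at HR 2.0, 91 at 1.8 and 191 at 1.5. At 50% possible MIBC this is 132, 182 and 382 recruits. These are rough, because a mixture does not have proportional hazards. For example, at HR 1.8 and 50 events the formula gives 54.7% power and the simulation 44.3%.

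**5. Size of the selection problem.** Of 10 true MIBC patients per arm, first TURBT labels at least 10 × (1 − 0.30) = 7 and mpMRI about 10 × 0.94 = 9.4.

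**The case against.** **Loose wording.** One could say that 13.3.2 writes MIBC as shorthand for possible MIBC. Its own secondary analysis, which contrasts possible with confirmed MIBC, and the 20-25% conversion in 13.2.2 rule that out. Nor is this a detail that can be left to a statistical analysis plan, since such a plan could not follow both definitions of the primary population.

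**MIBC is where the benefit is expected.** This is fair. It is a good reason to keep an MIBC analysis, but it does not make a group formed after randomisation the primary comparison.

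**MIBC might be confirmed the same way in both arms.** The protocol does not say that MRI alone confirms MIBC in pathway 2; the difference in tests is inferred from the pathway descriptions. Table 2 names histologically confirmed diagnosis as the reference for judging MRI and TURBT in the final stage. Sections 13.2.2 and 13.3.2, however, give neither a common definition nor a time point.

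**7 against 9.4 is a ceiling.** This is correct. Section 1.1 says up to 30% of MIBC, section 1.2 ties the figure to the highest-risk cases, and section 1.4 uses a different denominator, tumours assessed as high grade NMIBC. The figure also describes first staging only.

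**Stronger readings that the documents do not support.** A reader might infer that understaged pathway 1 patients need a repeat TURBT, have the longest TTDT, and drop out of the MIBC group, so that the analysis hides the delay. Section 13.1 stops the TTDT clock at the first TURBT, so a repeat TURBT cannot lengthen TTDT as defined. A reader might also infer stage migration in the 13.4 subgroup "Final diagnosis type: MIBC or NMIBC". That variable is the final diagnosis and may include later upstaging, and the subgroup by initial diagnosis is already planned.

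**Conclusion.** The contradiction is certain. The synopsis and Table 2 set the intermediate primary outcome in possible MIBC, while 13.3.2 analyses MIBC and 13.2.2 powers it. The MIBC comparison is not between groups as randomised, because status is settled after allocation along routes that differ by arm and no arm-neutral definition is given.

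The selection difference could reach 7 against about 9.4 of 10 at first staging, as an upper figure. The direction of any resulting bias in TTDT is not established.

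The 80% power does not carry over to the declared primary population. At 80-100 recruits it is roughly 20-60% with equal non-MIBC timing in both arms, and lower if pathway 2 delays TURBT in that part. This range assumes two-sided 5%, all MIBC lying within possible MIBC, the 100- and 70-day medians of 13.2.2, and non-MIBC medians of 30 to 100 days. The 100-day median is itself hard to square with a clock that stops at the first TURBT.

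**What to change.** - **13.3.2:** make the primary comparison all patients randomised as possible MIBC (boxes B and D), as in Table 2. Keep confirmed MIBC as supportive, with one reference definition and one time point applied to both arms.
- **13.2.2:** state that HR 3.6, 20 events and 80% power refer to the MIBC subset. Add the power for possible MIBC, with the assumed timing of non-MIBC patients given as a range.
- **13.1 and 13.2.2:** reconcile the TTDT definition, which counts TURBT as an end point, with the 100-day pathway 1 median.

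The cost is more than wording. Patients without MIBC dilute the effect, so either the stated power becomes less favourable or the look moves later and gives less early warning. The planned 950 patients would include about 950 × 50% = 475 possible MIBC, so a later look fits within planned recruitment if the trial continues to the final stage. No patients are added.
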